### **Secondary Aims/Hypotheses:**

1. To test the effects of the intervention on intermediate smoking variables including number of cigarettes smoked and number of quit attempts at 6 months following randomization.

Hypothesis 1A: At 6 months following randomization, among those who continue to smoke, participants in the

**I-ANBL** group will show a greater reduction in the number of cigarettes smoked than participants in the **I-FV** group. Mixed models for repeated measures will be used to examine the change in the number of cigarettes smoked over the 6-month study period. To evaluate group differences of reduced cigarette numbers, the models will examine the main effects of time, treatment, and the number of cigarettes smoked at baseline and their interactions. Estimated means at 6 months, which are adjusted for the baseline cigarette numbers, will be reported and compared between the groups.

Hypothesis 1B: Smokers receiving I-ANBL will make greater number of serious quit attempts than smokers receiving I-FV. We will compare the number of quit attempts between the two groups using Poisson regression for count data. In the Secondary Aim 1 analyses, the dropouts will be handled by multiple imputation as described in Primary Aim.

2. To compare differences between **I-ANBL** and **I-FV** in adherence rates to program participation at 6 months following randomization.

Hypothesis 2: At 6 months following randomization, participants in the I-ANBL group will have significantly higher adherence rates than smokers in the **I-FV** group.

We will summarize and compare the measures of program exposure and dose between the groups by descriptive statistics and the *t*-test or chi-square test. Then, we will examine group differences in adherence rates by modeling the binary outcome (dropouts vs. completers) with logistic regression.

**Data Management:** Survey data will be entered into the REDCap system through our website directly by participants or, in the case of the initial interview, the facilitator while s/he is asking the questions. REDCap is an internet-based survey program that allows de-identified and encrypted data to be collected directly on a site. We have used this program in other studies and our Human Subjects Committee has determined that it is a safe and effective way to collect data remotely. It also allows the creation of separate databases for contact information so that we can maintain a numeric study-specific participant number as the only link between the study database and participant contact information. Data management activities will include conversion into proper format for data analysis and recoding. All data management activities will be supervised by [name].

**Cost-effectiveness analysis:** The purpose of our cost-effectiveness analysis is to establish the cost-effectiveness of the I-ANBL program relative to healthy heart diet intervention. While our cost analytic

framework follows the guidelines adopted by the CDC, we will assess costs from the service provider perspective rather than the recommended societal perspective. Given that there is widespread agreement that

the cessation of smoking behavior confers important societal benefits valued far in excess of the costs needed

to produce them, the research expenses needed to fulfill the societal perspective would exceed the benefit of

that approach. Instead, variable costs for each study arm will be valued in the year during which they are incurred. Discounting is not required for the six month intervention period, and research costs (\$20 gift cards) will be excluded from analyses.

Program costs that will vary depend on the number of participants include, personnel time, internet charges, materials (brochures and other handouts), pharmacotherapy, and participant incentives. Research assistant time for session support will be documented using a time diary/log and valued at wage rates including benefits. Phone charges for local and long distance calls will be applied to the time for telephone-based counseling. Pharmacotherapy costs will be valued according to IHS medication costs inclusive of dispensing fees. For sensitivity analyses, we will vary pharmacotherapy costs according to prevailing retail rates (market value) using the average of no fewer than three price sources (local pharmacy as well as on-line pharmacy options). Mailing costs will be added. Items included as incentives will be valued at their retail prices.

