## **V. Study Procedures**

### **Design Overview**

The proposed study is a randomized design in which Tribal College smokers will receive one of two internet-based interventions: 1) a culturally and individually tailored, interactive smoking cessation intervention (**I-ANBL**); or 2) internet-based healthy diet -fruit and vegetable consumption intervention (**I-FV**). Participants in both groups (I-ANBL and I-FV) will be offered pharmacotherapy (e.g. varenicline or bupropion or NRT). The primary outcome of interest will be biochemically verified continuous abstinence at 6 months. Secondary endpoints include number of quit attempts and number of cigarettes smoked (among continuing smokers), pharmacotherapy utilization, and the number of completed web-sessions. We will also examine the marginal cost-effectiveness of the intervention.

We propose the adaptation and testing of a culturally tailored smoking cessation program for tribal college students. We will finish developing the program using an iterative, CBPR process that we have used in the past to develop a successful smoking cessation program for AI.

The study will be done in three phases over a five-year period. Phase 1 will include adaptation of the program and tailored materials, including assessments of the website for scientific

accuracy, readability, cultural appropriateness, and navigability; Phase 2 will be to conduct the randomized trial and Phase 3 will consist of data analysis and dissemination.

Participants will be recruited from a Tribal college.

**Pharmacotherapy:** The PI of this study along with our AI community members agreed that all participants (I-ANBL and I-FV arms) had to be offered pharmacotherapy (varenicline or bupropion or NRT) as a component of the study design. This decision was a collaborative one between the AI tribes and the investigators who have worked with this population. The AI community will not accept placebo treatment, therefore, the interventions would not be acceptable or feasible to potential participants if a placebo was part of the study design.

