**Phase 2: Delivery of Interventions**

The objectives of this phase are to: (1) recruit and screen participants for eligibility into study; (2) randomize tribal college students into the two arms (**I-ANBL** or **I-FV**); and (3) implement interventions and follow-up. We will recruit and randomize 300 tribal college smokers into two groups – the culturally-tailored arm (**I-ANBL** + offered varenicline/bupropion/NRT) and the heart healthy arm (**I-FV** + offered varenicline/bupropion/NRT).

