### Phase 3: Data Analysis and Dissemination

The objectives of this phase are 1) to conduct data analysis and 2) to disseminate the program.

In Year 5, we will complete post-intervention assessments, data analyses and report writing.

Process and outcome data will be presented at scientific conferences and manuscripts will be submitted to peer-reviewed scientific journals. Ultimately, we envision that **I-ANBL**, if efficacious, could be disseminated and

used as a culturally tailored smoking cessation intervention that could be adopted across different tribal colleges.

**Sample Size and Power:** The primary endpoint will be cotinine verified 7-day point prevalence abstinence at Month 6. Per preliminary findings, we expect a 30% cessation rate in the **I-ANBL** arm and a 15% cessation rate in the **I-FV** arm. Using the chi-square test, and the assumptions above, 121 participants in each group will give us 80% power to detect this difference with a type I error rate of 5%.

Given retention rates from our earlier studies, we expect attrition rates to be approximately 20% over the 6 month study period. Therefore, we anticipate needing to enroll 300 participants at baseline in order to have 242 active participants at 6 months.

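### Hypothesis 1A tests cigarette reduction only among participants still smoking at 6 months, a post-randomisation subgroup tied to the primary outcome, so it cannot by itself support a statement about the effect of the intervention

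*Protocol*

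**What the plan says.** The restriction to continuing smokers appears in three places in the protocol.

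- **Secondary Aims/Hypotheses, Hypothesis 1A:** "At 6 months following randomization, among those who continue to smoke, participants in the" I-ANBL arm are predicted to reduce their cigarettes more than those in the I-FV arm.
- **I. Rationale and Specific Aims, secondary aims table:** the same hypothesis with the same restriction.
- **Design Overview:** a secondary endpoint is the "number of cigarettes smoked (among continuing smokers", with the restriction in parentheses.

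Secondary Aim 1 itself has no such restriction and is worded as a test of what the intervention does to smoking variables. The planned analysis is a repeated-measures mixed model, with 6-month means adjusted for baseline cigarettes and dropouts multiply imputed. The protocol gives no analysis of cigarettes in all randomised participants and no caution that the subgroup contrast is not randomised.

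On the primary outcome, Sample Size and Power says: "The primary endpoint will be cotinine verified 7-day point prevalence abstinence at Month 6". It adds "we expect a 30% cessation rate in the" I-ANBL "arm and a 15% cessation rate in the" I-FV arm.

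**The concern.** Randomisation balances the arms as allocated. It does not balance the people left after those who quit have been removed, when the treatment is meant to change who quits. If I-ANBL works, some of its participants who would otherwise have gone on smoking leave the comparison as abstainers, while their counterparts in I-FV stay in it. If such people also tend to cut down more when they do not quit, the I-FV subgroup looks better for reasons unrelated to treatment.

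The imbalance grows with success on the primary endpoint. What is at stake is the reading of Secondary Aim 1: a contrast between two differently selected groups would be reported as an intervention effect.

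**Working it through.** **Inputs from the protocol.** Abstinence 30% v 15%; "Using the chi-square test, and the assumptions above, 121 participants in each group"; "80% power to detect this difference with a type I error rate of 5" per cent (all from Sample Size and Power). Phase 2 adds: "We will recruit and randomize 300 tribal college smokers into two groups", which is 150 per arm in the participant flow table.

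**Step 1: reproduce the plan's own figure.** Two-sided 5%, pooled variance, no continuity correction, mean rate (0.30 + 0.15)/2 = 0.225:

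n = [1.960 × √(2 × 0.225 × 0.775) + 0.842 × √(0.30 × 0.70 + 0.15 × 0.85)]² / 0.15² = (1.157 + 0.489)² / 0.0225 ≈ 120.5, so 121 per group (power 80.2%).

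The stated figure reproduces. The protocol states no figure for Hypothesis 1A.

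**Step 2: who stays in the comparison.** Continuing smokers are 1 − 0.30 = 70% of I-ANBL and 1 − 0.15 = 85% of I-FV. That is 105 v 127.5 of 150 per arm, or about 85 v 103 of 121.

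Assume I-ANBL stops nobody from quitting who would otherwise have quit. Then 15% of participants quit under either arm, 15% quit only under I-ANBL, and 70% smoke under either. The middle group is absent from the I-ANBL subgroup but makes up 0.15/0.85 = 17.6% of the I-FV subgroup.

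**Step 3: size of the shift.** Suppose that middle group, when in I-FV, cuts down by d cigarettes/day more than the other continuing smokers, and that the true benefit in those who smoke under either arm is e. The expected contrast (I-ANBL minus I-FV reduction) is then e − 0.176 × d. The protocol gives no value for d, so a range is shown:

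| d (assumed) | shift against I-ANBL, cigarettes/day |
|---|---|
| 0 | 0 |
| 1 | 0.18 |
| 2 | 0.35 |
| 3 | 0.53 |
| 5 | 0.88 |

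The sign of a true benefit reverses only if d > e × 0.85/0.15 = 5.67e. For e = 0.25 this means d > 1.4, and for e = 0.5, d > 2.8.

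**Step 4: does baseline adjustment remove it?** Simulated trials with 120 per arm, quitting 30% v 15%, and no true effect on reduction among continuing smokers. Assumed: baseline gamma-distributed with mean 10 cigarettes/day, and a follow-up/baseline ratio distributed beta(2,1). Continuing smokers were compared by analysis of covariance on baseline.

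| correlation of quitting with tendency to cut down | bias against I-ANBL, cigarettes/day | significant in the wrong direction |
|---|---|---|
| 0 | about 0 | about 2% |
| 0.3 | 0.16 | 6% |
| 0.5 | 0.25 | 10% |
| 0.7 | 0.40 | 21% |
| 1 (perfect link) | 0.56 | 55% |

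The chance rate in the last column is 2.5%. At a baseline mean of 5/day the bias halves (0.29 for the perfect link), while the significance rates stay the same.

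A second model used an unmeasured motivation factor, a baseline mean of 10 and 400,000 per arm. With no true effect it gave a baseline-adjusted bias of 0.10, 0.16 and 0.21 for correlations of 0.3, 0.5 and 0.7 between that factor and quitting, and about 0 with none. Adjustment for baseline cigarettes therefore leaves the bias in place, because the selection acts on something baseline cigarettes do not measure.

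**The case against.** Several points on the other side carry weight.

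- **Wrong-way results.** A reader might infer that the contrast will probably show harm. The documents do not support that. The 55% figure needs quitters to be exactly the largest reducers. In the second model a true benefit of 0.25 cigarettes/day is diluted to 0.15, 0.10 and 0.03 at correlations of 0.3, 0.5 and 0.7, but on average is not reversed.
- **Baseline level.** Ten cigarettes/day is assumed. Eligibility Requirements admits anyone who smoked one cigarette in the past 30 days, and the pilot results in section II describe this population as lighter smokers, so the bias in cigarettes/day may be smaller.
- **A real reduction hidden.** A reader might also infer that a genuine overall reduction would be lost. In the simulations the all-randomised gain (about 0.7 to 1.0 cigarettes/day in the first model) comes entirely from quitters set to 0. That is the cessation effect, which the primary endpoint already tests.
- **Dropouts.** It is tempting to say that a dropout's subgroup membership is undefined. Option (c) under Primary Aim/Hypotheses imputes abstinence for all participants, so each completed data set can assign it. That point is not pressed.
- **A different question.** Whether people who do not quit at least smoke less is a fair question, and an all-randomised analysis does not answer it alone. This stands, and is why the subgroup comparison should be kept.
- **Model wording.** The sentence describing the mixed model does not repeat the restriction, and the simulation used a single time point. But the hypothesis under test and the Design Overview both state the restriction, and a repeated-measures model confined to the same people inherits the same selection.

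None of this makes the contrast randomised.

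**Conclusion.** The point holds as a structural one. The only stated test of cigarette reduction conditions on a status that treatment is expected to change, so it cannot alone carry the causal wording of Secondary Aim 1. The 70% v 85% split follows directly from the protocol's rates; the 17.6% also needs the assumption in Step 2.

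Bias arises only if quitting is related to the tendency to cut down beyond what baseline cigarettes explain. If higher quitting goes with more cutting down, it runs against I-ANBL. Its size depends on d, on that correlation and on the baseline level, none of which the document supplies. This concerns one secondary endpoint; the primary comparison and the sample size are untouched.

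**What to change.** In Secondary Aims/Hypotheses, add a baseline-adjusted comparison of cigarettes/day at 6 months in all randomised participants, with abstainers counted as 0. Use a method suited to the excess of zeros, such as a linear model with robust standard errors, or a two-part model summarised as one overall mean difference. The smokers-only part of a two-part model is again the subgroup contrast and should not be read alone. Rest any causal statement for Secondary Aim 1 on the all-randomised comparison.

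Keep the continuing-smoker comparison, labelled descriptive and non-randomised, and carry the label into the aims table and the Design Overview.

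The cost is wording only: the Schedule of Assessments already collects cigarettes/day from everyone through 6 months. The downside is that the all-randomised estimate combines quitting with reduction and overlaps with the primary endpoint. A favourable result on it does not show that continuing smokers cut down, so the two analyses must be reported side by side.

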### **Statistical Analyses:**

We will first summarize all baseline measures globally and by treatment group. Categorical variables will be presented by frequencies and percentages within each of the possible categories and quantitative variables will be presented by means and standard deviations. Then, generalized linear modeling and mixed modeling will be applied to hypothesis testing for the primary and secondary aims (see below). In addition, for the exploratory purpose, we will evaluate potential covariates including smoking history and demographic, psychological, and sociocultural factors that may contribute to smoking abstinence. Interactions between intervention and these factors will also be investigated (i.e., moderation). All analyses will be conducted using SAS 9.2.

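### Hypothesis 1B fixes Poisson regression for quit attempts with no provision for a variance that differs from the mean, so the test could be anti-conservative or conservative

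*Protocol*

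**What the plan says.** Hypothesis 1B, under Secondary Aims/Hypotheses, is directional: "Smokers receiving I-ANBL will make greater number of serious quit attempts than smokers receiving I-FV". The test follows directly: "We will compare the number of quit attempts between the two groups using Poisson regression for count data". Missing data are covered in the next sentence: "In the Secondary Aim 1 analyses, the dropouts will be handled by multiple imputation as described in Primary Aim".

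The only other text on method is in Statistical Analyses, where "generalized linear modeling and mixed modeling will be applied to hypothesis testing for the primary and secondary aims". That names a model family but no variance estimator. The protocol does not provide for extra-Poisson or sub-Poisson variation, and it does not rule such a provision out. It reports no mean, variance or pilot distribution of quit attempts and sets no significance level for Hypothesis 1B. The 5% level under Sample Size and Power belongs to the abstinence endpoint.

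**The concern.** A Poisson likelihood sets the variance equal to the mean. Taken literally, the text yields a standard error that is correct only if quit attempts behave that way, and nothing in the protocol supports that.

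There are reasons to doubt it in both directions.

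- **Overdispersion.** Smoking status is self-defined in the inclusion criteria, and one cigarette in 30 days is enough under Eligibility Requirements. Users of other tobacco products are not excluded, and each participant chooses among several drugs or none. People who differ this much may differ in how often they try to quit. Sustained quitters will also be mixed with smokers who relapse and try again.
- **Underdispersion.** Session 2 is the quit date for everyone, and the participant flow lists it in both arms. Many participants could then record about one attempt, which bunches the counts.

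In the first case the intervals are too narrow and a claim of more quit attempts may be false. In the second they are too wide and a real difference may be missed.

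**Working it through.** **1. The plan's own figure.** The only sample-size calculation is for abstinence: "we expect a 30% cessation rate in the I-ANBL arm" and "a 15% cessation rate in the I-FV arm", and "121 participants in each group will give us 80% power to detect this difference with a type I error rate of 5" per cent. With a mean proportion of 0.225, a two-sided 5% level and no continuity correction:

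n = [1.96·√(2·0.225·0.775) + 0.8416·√(0.30·0.70 + 0.15·0.85)]² / 0.15² = (1.1575 + 0.4889)² / 0.0225 ≈ 120.5, so 121 per arm.

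This reproduces the plan; power at 121 per arm is 80.2%. Allowing for 20% attrition, 242/0.80 = 302.5, so 303 against the 300 stated, which is close enough. None of this bears on Hypothesis 1B, for which the protocol states no figure.

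**2. Inputs for 1B.** The model is Poisson regression (Secondary Aims/Hypotheses). The variance/mean ratio φ is not given, so a range is assumed. The level is assumed to be two-sided 5%.

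**3. Formula.** With totals S₁ and S₀ in the two arms, the model-based variance of the log rate ratio is 1/S₁ + 1/S₀. If both arms have ratio φ, the true variance is about φ times that. The actual type I error is then

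2·[1 − Φ(1.96/√φ)].

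**4. Results.** The simulation used 20,000 runs per scenario, 121 and 150 per arm, and means of 1, 2 and 3 attempts. Counts were binomial for φ below 1, Poisson at 1 and negative binomial above 1. Data were complete and there was no covariate.

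| Assumed φ | 1.96/√φ | Type I error, formula | Type I error, simulation |
|---|---|---|---|
| 0.5 | 2.77 | 0.6% | 0.5–0.6% |
| 0.8 | 2.19 | 2.8% | not run |
| 1.0 | 1.96 | 5.0% | 4.6–5.2% |
| 1.2 | 1.79 | 7.4% | not run |
| 1.5 | 1.60 | 11.0% | 10.6–11.3% |
| 2 | 1.39 | 16.6% | 16.3–17.0% |
| 3 | 1.13 | 25.8% | 25.1–25.9% |
| 4 | 0.98 | 32.7% | 32.2–32.9% |

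In the same simulated datasets, with φ from 0.5 to 4, a sandwich variance gave 4.9–5.8% and a Pearson-scaled variance 4.8–5.5%.

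**5. How much heterogeneity would it take?** If people differ in their underlying rate with coefficient of variation CV, then φ = 1 + mean × CV². At an assumed mean of 2 attempts, CV = 0.5 gives 1 + 2·0.25 = 1.5, and CV = 0.7 gives 1 + 2·0.49 ≈ 2. Ratios of 1.5 to 2 therefore need only moderate differences between people, though the protocol has no data to confirm them.

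**6. Imputation.** The protocol expects attrition: "we expect attrition rates to be approximately 20% over the 6 month study period". Multiple imputation adds between-imputation variance to the average within-imputation variance. The within part comes from each fitted model, so a misstated Poisson variance carries through. The complete-data percentages above would shift somewhat under the planned analysis.

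**The case against.** The strongest objection is that Poisson regression can be run with a robust or scaled variance, that the protocol's sentence does not exclude this, and that such an option is often left to the statistical analysis plan. The recommended fix fits the quoted sentence unchanged. This stands in part: model-based errors are the literal reading, not a stated choice. It does not dispose of the point. The protocol fixes the distribution for a named efficacy hypothesis, and the distribution brings a variance assumption that its own design makes doubtful in either direction.

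A reader might infer that the type I error for 1B is inflated, or at least that it is not 5%. The documents do not support that. They give no dispersion figure; at a ratio of 1 the error is 5%, and heterogeneity and the common quit date could roughly cancel. Nor do they support a one-sided warning about false positives, because with bunched counts the test is conservative.

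Three further objections hold. Eligibility describes how much people smoke, not how often they try to quit, so overdispersion is an inference. The calculations use complete data, not the planned imputation. Adjusting for earlier quit attempts is not needed to control the type I error in a randomised comparison and does not cure a wrong variance.

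**Conclusion.** The concern holds in conditional form. The protocol fixes Poisson regression for quit attempts and makes no provision for a variance that differs from the mean. If model-based errors are used, the type I error runs from about 0.6% at a ratio of 0.5, through 5% at 1, to about 26% at 3.

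This rests on assumed ratios that are equal in both arms, an assumed two-sided 5% level for 1B, complete data and no covariates. The direction cannot be settled from the documents. Confidence is moderate. Only a secondary aim is affected, and the abstinence comparison is untouched. The point is still worth acting on, because a better-behaved method costs almost nothing.

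**What to change.** Replace the sentence on the test for Hypothesis 1B with, for example:

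*The number of serious quit attempts will be compared between arms by Poisson regression with a robust (sandwich) or Pearson-scaled variance, fitted within each imputed dataset and combined across imputations, adjusted for the number of quit attempts in the past year recorded at week 1.*

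One of the two variance estimators should be chosen in advance. In the complete-data simulation both held about 5 to 6% whether counts were under- or overdispersed. Negative binomial regression alone is not enough, because its variance cannot fall below the mean and so it does not handle bunched counts. The covariate is already in the assessment schedule under quitting history; its purpose is precision.

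The cost is one sentence and a different option in the same modelling procedure, with no new data. The downside is slightly less efficient intervals if the counts are truly Poisson; in that case the sandwich test still gave 4.9–5.3% in simulation.

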## Measures

**Schedule of Assessments:** The table below represents our preliminary listing of outcome assessments, based on measures used for ANBL and preliminary discussions with community members. During year one of the project, we will work closely with our community partners to refine all measures and potentially add or subtract some of them. Our community partners will have final say on all measures to be used, including whether we use standard measures validated in other populations or modify for our community.

Measures Week	1	2	3	4	5	6	7	8	12	6 mo
Primary Outcome										
The primary endpoint for the study will be biochemically (salivary cotinine) verified point prevalence abstinence, defined as no smoking for the previous 7 days, at the 6-month follow-up. This definition is based on recent consensus statements from the Society for Research on Nicotine and Tobacco Subcommittee on Abstinence Measures.	X								X	X
Biochemical Validation	X								X	X
Pharmacotherapy Use		X	X	X	X	X	X	X	X	
Demographics Tribal affiliation, age, gender, marital status, income, year in school	X									
Smoking behavior										
Traditional use of tobacco	X	X	X	X	X	X	X	X	X	X
Smoking history (age of initiation)	X									
Quitting history (length of most recent quit attempt, number of quit attempts in the past year)	X									
Self-reported Smoking status (number of cigarettes/day)	X	X	X	X	X	X	X	X	X	X
Nicotine Dependence - The Fagerstrom Test of Nicotine Dependence will be used to measure nicotine dependence. 	X								X	X
Self-efficacy	X			X				X	X	X
Motivation	X			X				X	X	X
Environmental factors										
Household structure	X								X	X
Social support	X								X	X

Exposure to others who use tobacco in any form	X			X		X			X	X
Exposure to tobacco marketing	X			X		X			X	X
Psychosocial factors										
Depression using the CES-D, 10-item. 	X		X		X		X		X	X
Negative Affect from the Positive and Negative Affect Scale (PANAS) , 	X		X		X		X		X	X
Nicotine Withdrawal using the Minnesota Withdrawal Scale (MNWS) 	X		X		X		X		X	X
Craving using the Brief Questionnaire of Smoking Urges (QSU-Brief) , 	X		X		X		X			
Treatment Factors										
Satisfaction with interactive website					X				X	X
Satisfaction with session topics		X	X	X	X	X	X	X	X	
Satisfaction with session educational materials	X	X	X	X	X	X	X	X	X	

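### Hypothesis 1B compares quit-attempt counts with no baseline term; adding the past-year count already collected at week 1, with robust or overdispersion-adjusted errors, may gain precision at almost no cost

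*Protocol*

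**What the plan says.** Hypothesis 1B (Protocol, section V, Secondary Aims/Hypotheses) reads: "Smokers receiving I-ANBL will make greater number of serious quit attempts than smokers receiving I-FV". Its analysis is a single sentence: "We will compare the number of quit attempts between the two groups using Poisson regression for count data". That sentence gives an outcome, a contrast and a model family. It gives no baseline covariate and no provision for overdispersion. It also does not call the model unadjusted.

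For Hypothesis 1A, in the same secondary aim, the terms are spelled out: "the models will examine the main effects of time, treatment, and the number of cigarettes smoked at baseline and their interactions". The reported result is "Estimated means at 6 months, which are adjusted for the baseline cigarette numbers".

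The Schedule of Assessments (Measures) lists "number of quit attempts in the past year" under quitting history, marked at week 1 only.

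The Statistical Analyses section has a general covariate statement: "we will evaluate potential covariates including smoking history and demographic, psychological, and sociocultural factors that may contribute to smoking abstinence". It is introduced as exploratory and concerns abstinence, so it does not supply a baseline term for 1B.

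**The concern.** People differ in how readily they try to quit. If those who tried often in the year before the trial also try more often during it, the past-year count explains part of the spread in the 1B outcome. A model that leaves it out estimates the rate ratio less precisely than it could, and any chance difference between arms in prior quitting stays in the estimate. Quit attempts are named in the secondary aims, and the covariate is already collected.

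At stake is efficiency on a secondary endpoint. Validity is not in question.

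**Working it through.** **Inputs from the protocol.** 121 per group (242 evaluable) for the primary endpoint, from Sample Size and Power. No mean, variance, correlation or power is given for quit attempts. Everything below about 1B therefore rests on assumed values.

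**The plan's own figure.** For 30% v 15%, two-sided 5%, 80% power, pooled variance:

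n = [1.96·√(2·0.225·0.775) + 0.8416·√(0.30·0.70 + 0.15·0.85)]² / 0.15² = (1.157 + 0.489)² / 0.0225 ≈ 120.5, so 121 per group.

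The figure reproduces (power at 121 is 80.2%). It says nothing about 1B beyond the number of people available.

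**Gain as a function of rho.** Approximate formulas, with rho the correlation between the baseline count and the outcome:

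- SE ratio = √(1 − rho²)
- Equivalent N = 242 / (1 − rho²)
- Power, if the unadjusted test had 80% = Φ[(1.96 + 0.8416)/√(1 − rho²) − 1.96]

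| rho (assumed) | SE reduction | Equivalent N | Power |
|---|---|---|---|
| 0 | 0% | 242 | 80.0% |
| 0.1 | 0.5% | 244 | 80.4% |
| 0.2 | 2.0% | 252 | 81.6% |
| 0.3 | 4.6% | 266 | 83.6% |
| 0.4 | 8.3% | 288 | 86.4% |
| 0.5 | 13.4% | 323 | 89.9% |

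Example at 0.5: √0.75 = 0.866, and 2.8016/0.866 − 1.96 = 1.275, so Φ = 0.899.

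**Simulation with counts.** Assumed: 121 per arm, control mean 1 attempt in 6 months, past-year mean 2, rate ratio 1.4, a gamma person effect (variance k) shared by both counts, and 600 runs per setting. Poisson regression was fitted with and without log(1 + baseline). Power uses robust errors.

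| Setting | Empirical SE without → with baseline | Power without → with | Model-based Poisson SE without → with |
|---|---|---|---|
| k = 0, rho ≈ 0 | 0.118 → 0.119 | 79% → 79% | 0.119 → 0.119 |
| k = 0.3, rho ≈ 0.29 | 0.138 → 0.132 | 69% → 73% | 0.120 → 0.120 |
| k = 0.8, rho ≈ 0.52 | 0.170 → 0.140 | 56% → 69% | 0.120 → 0.120 |

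**Why the last column does not move.** The model-based Poisson SE of a log rate ratio depends essentially on the event totals: √(1/121 + 1/(121·1.4)) = √(0.00826 + 0.00590) = 0.119, with or without a balanced covariate. With overdispersion the true unadjusted SE is larger. At k = 0.8 it is √(0.01417 + 2·0.8/121) = 0.166, in line with the simulated 0.170. The covariate lowers the true variability, but the reported plain Poisson interval shows none of it and is too narrow in either case.

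**The case against.** **The text is silent and states nothing wrong.** A reader might infer that 1B is fixed as unadjusted. The protocol does not say so, and the covariates of a secondary model are commonly left to a statistical analysis plan, which is not at hand. This stands. The point is an improvement to a stated choice.

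**The contrast with 1A is not an inconsistency.** A reader might infer that one aim treats two endpoints by conflicting rules. Hypothesis 1A is about reduction in cigarettes, so baseline enters naturally and on the same scale. Hypothesis 1B compares counts between arms. This stands too. The contrast shows only that baseline adjustment is already familiar to this plan.

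**The item is not a like-for-like baseline.** It covers any attempt over 12 months. The outcome is serious attempts during a trial that sets session 2 as the quit date for everyone (Internet Sessions 2-8). Attempts prompted by the programme may relate only weakly to earlier ones. This is a sound reason to expect a low rho, but it does not make adjustment improper: any pre-treatment prognostic variable may be used in a randomised comparison.

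**The covariate alone would not narrow the interval.** Correct for plain Poisson regression, as the working shows. The variance method has to change with it.

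**Another matter comes first.** The schedule marks the quit-attempt item at week 1 only, so how the follow-up count is obtained is unclear. That needs reconciling before the model is refined, but it is a separate point.

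**Conclusion.** The point holds as a minor, optional improvement. The 1B sentence names no baseline term, the covariate is already collected, and the general covariate statement does not cover this endpoint.

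The size depends wholly on an assumed correlation: an SE reduction of about 0% at rho 0, 2% at 0.2, 5% at 0.3 and 13% at 0.5. The lower part of that range is plausible for the reason given under the objection. At rho 0 the loss in simulation was negligible (SE 0.118 v 0.119).

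A reader might conclude that precision is certainly being given up. The documents do not support that, since they contain no correlation, mean or dispersion for quit attempts and rho could be near zero. What can be said is that precision may be gained, that chance imbalance in prior quitting would be corrected, and that the cost is one degree of freedom.

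**What to change.** In Secondary Aims/Hypotheses, Hypothesis 1B, state three things:

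1. The count model contains treatment and log(1 + past-year quit attempts at baseline).
2. Standard errors are robust (sandwich) or adjusted for overdispersion.
3. The adjusted rate ratio with its 95% confidence interval is the Hypothesis 1B result.

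Item 2 is needed for the reported interval to reflect any gain. With a log link and no treatment-by-baseline interaction, the adjusted and unadjusted rate ratios estimate the same quantity, so the question asked does not change.

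Cost: a sentence or two of text, one degree of freedom, and no new data.
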